5.4. Baseline Definitions

For 6-MWT, baseline will be defined as the last non-missing value available prior to the first dose of study drug.

For other efficacy parameters, baseline will be defined as the last non-missing value available on or before the date of first dose of study drug, unless otherwise specified.

For TTR, baseline will be defined as the average of all records collected on study, including those from any unscheduled visits, prior to the date and time of first dose.

For each parameter of the 12-lead electrocardiogram (ECG), baseline will be defined as the average of all available readings from the last visit prior to the first dose of study drug.

For all other parameters, baseline will be defined as the last non-missing value available prior to the first dose of study drug, unless otherwise specified.

For the All Patisiran Treated Set, baseline for patients who switched from placebo to patisiran will be redefined as:

- For TTR, the redefined baseline will be calculated as the mean of all TTR assessments performed on or after Month 9 in the 12m-DB period and prior to the first dose in the OLE period.
- For all the other endpoints, the redefined baseline will be defined as the last non-missing value available on or after Month 9 in the 12m-DB period and prior to the first dose in the OLE period, unless otherwise specified. For longitudinal efficacy endpoints, if a patient does not have a Month 12 assessment prior to the first dose in the OLE period, the redefined baseline will be defined as the last non-missing value available on or after Month 9 in the 12m-DB period and up to 3 weeks after the first dose in the OLE period, unless otherwise specified.

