5.6. Visit Windows

Scheduled visits are expected to follow the protocol schedule. All data will be tabulated and analyzed per the evaluation visit as recorded on the electronic case report form (eCRF) even if the assessment is outside of the visit window.

For 6-MWT and KCCQ, assessments will be conducted at baseline and at Months 6, 9, and 12 in the 12m-DB period and at Months 18, 21, 24, 30, 33, 36, 42 and 48 in the OLE period. For all longitudinal efficacy assessments, if a scheduled post-baseline assessment is not performed, assessments performed within ± 1.5 months of the scheduled assessment will be grouped with the scheduled assessments for that timepoint for analysis, with the following exception:

- For patients randomized to placebo who received patisiran in the OLE period, assessments performed after the first OLE dose will not be grouped with the scheduled Month 12 visits even if they are within ± 1.5 months.

The derived visits will be used for all analyses.

Unless otherwise specified above, data collected at unscheduled visits will be included in by-patient data listings and figures but no assignment to a study visit will be made for the purpose of by-visit summary tabulations. However, unscheduled visits may be used in the calculation of baseline values (as discussed in Section 5.4) and for inclusion in any categorical shift summaries (eg, shift from baseline to “worst” post-baseline value).

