5.11. Analyses for the Entire Study

The study design includes a 12m-DB period and an OLE period. The primary objective is to evaluate the efficacy and safety of patisiran compared with placebo during the 12m-DB period. In addition, the long-term efficacy and safety of patisiran during the entire patisiran treatment period (beyond 12m-DB) will be characterized for the All Patisiran Treated Set.

The detailed definitions for different treatment periods are as follows.

- **12m-DB Period**

The treatment comparison of patisiran versus placebo will focus on the 12m-DB period, defined as below:

1. For patients who received at least one dose of patisiran during the OLE period, all assessments collected prior to the first dose of patisiran in the OLE period will be included in the 12m-DB period. For patients randomized to patisiran, longitudinal efficacy assessments after the first OLE dose may be included in the 12m-DB period analyses as described in Section 5.6.
2. For patients who discontinued treatment and did not receive any patisiran doses in the OLE period, all assessments will be included in the 12m-DB period. Assessments collected within given time windows (details listed in below table) will be included in summary tables/figures and those outside the time windows will be listed only, unless otherwise specified (eg, AEs in Section 6.9).

Endpoint	Windowing rule for patients who did not enter OLE
Hospitalization/urgent HF visit/death	Events occurring on or before Day 417
Other efficacy endpoints	Assessments collected on or before Day 417
PK/PD endpoints	Assessments collected within 28 days of the last dose
Safety endpoints	Assessments with onset date within 28 days of the last dose ^a

^a In the rare situation where a patient did not discontinue treatment in the 12m-DB period and did not enter the OLE period, all data will be included in the summary tables/figures. For AE summaries, related AEs will be considered treatment-emergent and included in summary tables regardless of time window.

- **OLE Period**

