7.4. Changes in SAP Amendment 2.1

SAP Amendment 2.1 addresses regulatory feedback received from the FDA on SAP Amendment 2. The main changes in SAP Amendment 2.1 include an update to the population-level summary estimate for 6-MWT and a change to the imputed 6-MWT distance for patients who die or who lose the ability to walk due to progression of ATTR amyloidosis. The details of the main changes, including other additional updates, and rationales for the changes are listed in the table below.

Summary of Changes	Detailed Description/Rationale
Updated population-level summary estimate from unstratified Hodges-Lehmann estimate to stratified Hodges-Lehmann estimate	Update made following regulatory feedback to use HL estimate stratified by baseline tafamidis use, which is consistent with the planned stratified Wilcoxon rank sum test.
Updated imputed values for patients who die or who lose the ability to walk due to progression of ATTR amyloidosis	Update made following regulatory feedback. For the primary analysis of 6-MWT, patients who die or who lose the ability to walk due to progression of ATTR amyloidosis will now be imputed as the worst 10 th percentile change observed across all patients in the 12m-DB period, capped by the worst possible change for the patient (ie, 0 – baseline 6-MWT). This is expected to be less influential on the estimated treatment effect than simply imputing the worst possible change for these patients.
Added condition that 6-MWT assessments where the timer was stopped after ≤ 4 minutes will be excluded from analyses	Exclude assessments that were improperly conducted
Updated windowing rule for longitudinal efficacy assessments for patients randomized to patisiran	To allow assessments collected shortly after first OLE dose to be summarized with Month 12 assessments in order to reduce the amount of missing data. Efficacy endpoints are not expected to be meaningfully impacted within a short time after the first dose in the OLE period.
Added treatment-by-baseline tafamidis use interaction term to echo and Norfolk ANCOVA models	To allow for potentially different treatment effects between the baseline tafamidis use (yes/no) subgroups.
Added Section 5.9	To clarify that the primary analysis for endpoints related to hospitalizations and urgent HF visits will be based on CEC adjudication results

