5.3. Visit Windows

CMR and technetium scintigraphy assessments will be conducted at baseline and Month 12 in the 12m-DB period and at Months 18, 24, 36, and 48 in the OLE period. For patients randomized to placebo, if the scheduled Month 12 assessment is not performed prior to the first dose of patisiran in the OLE period, assessments performed within ± 3 months of the scheduled assessment (eg, from an unscheduled visit) and prior to the first dose of patisiran in the OLE period will be grouped with the scheduled Month 12 assessments for analysis. The same windowing for Month 12 will be applied for patients randomized to patisiran, with the exception that assessments performed up to 6 weeks after the first dose of patisiran in the OLE period will be grouped with the scheduled Month 12 assessments for analysis; this window was extended since these endpoints for patisiran patients are not expected to be meaningfully impacted within a short time after the first dose in the OLE period. For assessments in the OLE period, if a scheduled post-baseline assessment is not performed, assessments performed within ± 3 months of the scheduled assessment will be grouped with the scheduled Month 18, 24, 36, or 48 assessments for analysis. The derived visits will be used for all analyses.

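### Month 12 can include open-label assessments in the patisiran arm only, and no sensitivity analysis tests that rule

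*SAP*

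**What the plan says.** The text in force is the main SAP, Amendment 2.1.

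- **General rule (Section 5.6).** When a scheduled post-baseline efficacy assessment was not performed, "assessments performed within ± 1.5 months of the scheduled assessment will be grouped with the scheduled assessments for that timepoint for analysis".
- **Placebo arm (Section 5.6).** "For patients randomized to placebo who received patisiran in the OLE period, assessments performed after the first OLE dose will not be grouped" with Month 12, even inside the window.
- **Patisiran arm (Section 5.11, 12m-DB Period).** "For patients randomized to patisiran, longitudinal efficacy assessments after the first OLE dose may be included in the 12m-DB period analyses", with a pointer back to Section 5.6.
- **Reach (Section 5.6).** "The derived visits will be used for all analyses". This covers the primary 6-MWT test, the KCCQ-OS MMRM and step 3 of the win ratio, which are ranks 1 to 3 in the Section 5.7 hierarchy.
- **Reason (Section 7.4).** The change is listed as "Updated windowing rule for longitudinal efficacy assessments for patients randomized to patisiran". It is justified by having fewer missing data and by the statement that "Efficacy endpoints are not expected to be meaningfully impacted within a short time after the first dose in the OLE period".

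**The concern.** The extension is open label (Section 2.1). A patisiran patient assessed after the first extension dose knows that the current infusion is active drug. The 6-MWT depends on effort, and the KCCQ is self-administered (Appendix 9.3.1). The Section 7.4 reason speaks to what one more dose might do pharmacologically. It does not address what knowledge of current treatment might do to a walk or a questionnaire.

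Missing Month 12 values are also filled differently by arm. A late patisiran value counts as observed. A late placebo value is set aside and handled under MAR: multiple imputation for 6-MWT, the likelihood model for KCCQ-OS. Because Section 6.6.1.2 imputes separately by arm, the open-label patisiran values also inform the imputed patisiran values.

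None of the sensitivity analyses in Sections 6.6.1.3 and 6.6.2.1.3 removes these values or applies one cut-off to both arms. Section 5.8.1 counts missing data but not post-OLE-dose Month 12 values, so a reader of the results could not see how many there were. What is at stake is a possible small, unmeasured bias in the top-ranked confirmatory tests.

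**Working it through.** **1. The rule, side by side.** Scheduled Month 12 assessment not performed; another one made within the window but after the first OLE dose:

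| | Patisiran arm | Placebo arm |
|---|---|---|
| Treatment at that assessment | patisiran, as assigned | patisiran, switched |
| Setting | open label | open label |
| Counts as Month 12? | may be included (5.11) | no (5.6) |
| Otherwise | not applicable | MI (6-MWT), MMRM (KCCQ-OS), latest common visit (win-ratio step 3) |

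The window is 1.5 × 30.4375 = 45.7 days, just over two 21-day dosing intervals (45.7 / 21 = 2.2).

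**2. The plan's own power figure (Section 5.1).** Weighted difference 0.7 × 33 + 0.3 × 20 = 29.1 m, stated as 29 m. SD 75 m, 150 per arm, two-sided alpha 0.05.

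- SE = 75 × √(2/150) = 8.66 m.
- Power = Φ(29/8.66 − 1.96) = 91.8%. The stated figure of more than 90% is reproduced.

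**3. Possible bias in 6-MWT.** The SAP gives neither the share of patisiran Month 12 values taken after the first OLE dose nor the shift in such values. Both are assumed here.

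- Bias = share × shift.
- SE for the rank test, taking normal data for illustration: 8.66 × √(π/3) = 8.86 m.
- Two-sided error with no true effect = 1 − Φ(1.96 − bias/SE) + Φ(−1.96 − bias/SE).

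| Share | Shift | Bias | % of 29 m | Two-sided error |
|---|---|---|---|---|
| 2% | 10 m | 0.2 m | 0.7% | 5.01% |
| 5% | 10 m | 0.5 m | 1.7% | 5.04% |
| 5% | 30 m | 1.5 m | 5.2% | 5.3% |
| 10% | 20 m | 2.0 m | 6.9% | 5.6% |
| 10% | 30 m | 3.0 m | 10.3% | 6.3% |
| 20% | 30 m | 6.0 m | 20.7% | 10.4% |

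With the SE of 8.66 m the last two rows become 6.4% and 10.7%. No KCCQ-OS figure is offered, because the SAP gives no SD or effect size for it.

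**4. Cost of a common cut-off.** Take the worst case, in which every excluded patisiran value is simply lost. SE = 75 × √(1/150 + 1/n), where n is the number of patisiran values remaining.

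| Patisiran values lost | Power, SE as in Section 5.1 | Power, SE × √(π/3) |
|---|---|---|
| 0% | 91.8% | 90.5% |
| 5% | 91.1% | 89.8% |
| 10% | 90.3% | 89.0% |
| 20% | 88.4% | 87.0% |

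On the plan's own basis the target of more than 90% survives a loss of about 10% of the patisiran arm. On the rank-test SE a 10% loss costs about 1.5 points. Multiple imputation from Months 6 and 9 would recover part of this.

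**The case against.** The case for the rule as written is substantial.

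- **The arms are not in the same position.** After the first OLE dose a placebo patient has switched to patisiran, while a patisiran patient is still on the assigned drug. A reader might infer from the asymmetry that the placebo exclusion is arbitrary. It is not: the estimand compares patisiran with placebo, and a common cut-off keeps that exclusion.
- **It is limited and declared.** It applies only when the scheduled assessment was not performed, it is prespecified, and a reason is given.
- **Direction.** A reader might infer that the rule favours patisiran. Expectation could push that way. A later walk in a progressive disease could push the other way. If visits ran late because patients were unwell, replacing observed poor walks by MAR imputation could itself flatter patisiran. The SAP does not settle the direction.
- **Blinding.** Starting the extension reveals the current drug. Nothing in the SAP says it reveals the randomized arm, and Section 2.3 restricts unblinding. The exposure is to expectation about current treatment, not knowledge of assignment.
- **Section 5.4.** Accepting placebo switchers' values "in the 12m-DB period and up to 3 weeks after the first dose in the OLE period" might be read as a contradiction. That is a fallback baseline for long-term summaries of the All Patisiran Treated Set, not a confirmatory comparison, so it is weak support.
- **Imaging SAP, Section 5.3.** It has a similar allowance, "with the exception that assessments performed up to 6 weeks after the first dose of patisiran in the OLE period". The argument does not carry over: extracellular volume and tracer uptake are neither effort-dependent nor self-reported, and these endpoints are exploratory.

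All of these points stand. They limit the size and reach of the concern. They do not answer two facts: the Section 7.4 rationale leaves out knowledge of treatment, and no planned analysis shows whether the rule matters.

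**Conclusion.** The concern holds in a limited form. Open-label values can enter the patisiran arm alone in the 6-MWT, KCCQ-OS and win-ratio step 3 comparisons, on a rationale that covers only drug effect, with no sensitivity analysis and no planned count.

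The size is unknown. Under the assumed 5-10% of patisiran values and a 10-30 m shift, the bias is 0.5-3.0 m and the two-sided error about 5.0-6.3%, if the shift runs in patisiran's favour. At 2% and 10 m it is negligible; it becomes large only if many patients are affected. The one-sided tail in patisiran's favour would read 2.9-5.3% against 2.5%, which might suggest a doubling of the error rate. The planned test is two-sided at 0.05, so the two-sided figure is the one to quote.

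This should be fixed. It does not by itself invalidate the primary analysis.

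**What to change.** 1. In main SAP Sections 5.6 and 5.11, state that for 6-MWT, KCCQ-OS and the win ratio no assessment after the first OLE dose is grouped with Month 12 in either arm. Superseded Amendment 2, Section 5.6, used this cut-off for 6-MWT and KCCQ in both arms, so it is workable.
2. Keep the current inclusive rule as a supportive analysis. Running both versions answers the choice between observed open-label values and MAR handling.
3. If the primary rule is kept, at minimum prespecify the common cut-off as a sensitivity analysis for all three endpoints.
4. Report the number of post-OLE-dose Month 12 values in the patisiran arm, for example with the missing-data summary in Section 5.8.1.

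The cost is a few sentences, one extra run per endpoint and a few more missing patisiran values. Those fall to methods already planned: multiple imputation for 6-MWT, the MMRM for KCCQ-OS and the latest common visit in win-ratio step 3. No change to the Imaging SAP is needed on this account.

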5.7. Multiple Comparisons/Multiplicity

Formal statistical hypothesis testing will be performed on the primary and secondary efficacy endpoints with all tests conducted at the nominal 2-sided 0.05 significance level. The overall familywise error rate will be controlled at the 2-sided 0.05 significance level for the primary and secondary endpoints by a hierarchical ordering procedure. Endpoints will be tested in the following pre-specified hierarchy:

1. 6-minute walk test (6-MWT) change from baseline at Month 12
2. Kansas City Cardiomyopathy Questionnaire Overall Summary (KCCQ-OS) score change from baseline at Month 12
3. Composite endpoint of all-cause mortality, frequency of CV events (CV hospitalizations and urgent HF visits), and change from baseline in 6-MWT over the 12-month double-blind period
4. Composite endpoint of all-cause mortality and frequency of all-cause hospitalizations and urgent HF visits over the 12-month double-blind period in patients not on tafamidis at baseline

5. Composite endpoint of all-cause mortality and frequency of all-cause hospitalizations and urgent HF visits over the 12-month double-blind period in the overall population

There will be no multiplicity adjustment for exploratory endpoints.

5.8. Missing Data with Efficacy Endpoints

5.8.1. Summary of Missing Data

For the 6-MWT and KCCQ-OS efficacy endpoints, the number and percentage of patients with missing data, including due to COVID-19, at each scheduled visit will be summarized by treatment arm.

Time to treatment discontinuation in the 12m-DB period will be estimated descriptively using the Kaplan-Meier method by treatment arm. Patients who receive at least 1 dose of patisiran in the OLE period will be censored at the date of first dose in the OLE period.

5.8.2. Handling of Missing Data

For 6-MWT, the primary analysis will be based on the stratified Wilcoxon Rank Sum test. For patients with missing data at Month 12 who die during the 12m-DB period (not due to COVID-19) or who have become unable to walk due to progression of ATTR amyloidosis by Month 12, the missing Month 12 6-MWT change from baseline will be imputed as the worst 10th percentile change observed across all patients in the 12m-DB period, capped by the worst possible change for the patient (ie, 0 – baseline 6-MWT). Missing data due to other reasons will be multiply imputed assuming data are missing at random (MAR). Data handling strategies for intercurrent events in the primary analysis of 6-MWT are detailed in [Table 1](#). Sensitivity analyses for 6-MWT will be conducted to assess the impact of missing data as discussed in [Section 6.6.1.3](#).

For KCCQ-OS, the primary analysis will be based on the mixed-effects model repeated measures (MMRM) method, which makes use of fully and partially observed data sequences from individual patients by estimating the covariance between data from different time points. The MMRM will be implemented using an unstructured approach to modeling both the treatment-by-time means and the (co)variances, leading to what is essentially a multivariate normal model wherein treatment arm means at the primary time point are adjusted to reflect both the actually observed data and the projected outcomes from the patients with missing data. [[Mallinckrodt 2008](#)] Data handling strategies for intercurrent events in the primary analysis of KCCQ-OS are detailed in [Table 3](#). In this primary analysis, missing data will not be explicitly imputed and are assumed to be MAR. Sensitivity analyses for KCCQ-OS will be conducted to assess the impact of missing data as discussed in [Section 6.6.2.1.3](#).

5.9. Categorization of Hospitalizations and Urgent HF Visits

For endpoints that include hospitalizations or urgent HF visits, the primary analysis will be based on events adjudicated by the Clinical Events Committee (CEC). The definitions for these events and the process of adjudication were prespecified in the CEC Charter. Specifically, the CEC adjudicates all non-elective CV and non-CV hospitalizations that result in at least 24-hour stay (or a change in calendar date if the hospital admission or discharge times are not available), as well as all urgent, unscheduled office or outpatient visits for heart failure (urgent HF visits).

Investigators also record their assessment of each inpatient admission or urgent/unscheduled healthcare visit on the eCRF. Hospitalizations and urgent HF visits based on the Investigator's assessment are defined as follows:

- Hospitalizations are defined as non-elective hospitalizations or visits requiring overnight stay (ie, discharge date at least one day after admission date). The exact times of admission/discharge are not collected in the eCRF; therefore, the 24-hour stay criteria cannot be applied. For each hospitalization, the investigator provides their classification of CV versus non-CV.
- Urgent HF visits are defined as events that are not classified as hospitalizations based on the above definition but do meet the following criteria:
 - Heart failure as the primary reason for the visit
 - IV diuretics administered during the visit
 - If the primary location for the visit is “Inpatient Admission”, the visit must be marked as non-elective per the Investigator.

Hospitalizations and urgent HF visits based on the Investigator's assessment will be summarized. In addition, the concordance between the CEC adjudication outcome and the Investigator's assessment will be summarized.

5.10. Analysis Cutoff and Database Lock

For the final 12m-DB analysis, as this study will be ongoing, the study database will be locked with all data up to a prespecified cutoff date quality controlled, ie, data in the electronic data capture (EDC) system will be frozen and external data such as laboratory and PK data will be quality controlled (and quality assured, where appropriate) and cleaned. Additional details regarding the database lock process are located in the study Data Management Plan.

The final 12m-DB analysis will include data on or prior to this prespecified cutoff date. Survival follow-up data after the cutoff date will be kept in the dataset in order to determine the survival status of patients at the time of cutoff. For assessments with starting/ending dates (eg, AEs, medications, medical history), the starting date will be compared with the pre-specified cutoff date.

After the study is completed, ie, all patients either discontinue or complete the study, the database will be hard-locked and all data collected will be used for analysis.

